8.10 Electrocardiograms

Twelve-lead ECGs will be obtained at screening, Days 1 and 8 (pre-dose and 30 ± 10 minutes after the end of infusion) and as clinically indicated within a window of ± 10 minutes. If the patient remains hospitalized, will also be performed on Days 15 and 29. Whenever ECG and blood samples are specified to be collected at the same time, ECG will be obtained before the blood samples. ECGs should be obtained in digital format when possible and archived.

Patients should be in a supine position for at least 10 minutes prior to the ECG measurement. The ECG measurements will include heart rate, RR-interval, PR-interval, QT-interval, QRS-complex, and QTcF.

8.11 Physical Examinations

A physical examination will be performed at screening, Days 1 and 8. If the patient remains hospitalized, will also be performed on Days 15 and 29. A complete physical examination will be performed at screening and Day 29 if the patient is hospitalized, while a symptom-directed physical examination will be conducted on Days 1 and 8, and Day 15 if the patient is hospitalized.

The physical examination will consist of assessments of general condition, skin, eyes/ears/nose/mouth/throat, neck/thyroid, chest/lungs, heart, vascular system, lymph nodes, abdomen, extremities, nervous systems/reflexes, musculoskeletal, and spine.

The patient's weight will be measured within 12 hours prior to dosing on each day of study drug administration.

8.12 Lung Function Assessments

Lung function will be assessed daily by peripheral capillary oxygen saturation (SpO₂) in ambient air (if possible), SpO₂ with oxygen supplementation (if applicable), documentation of oxygen delivery method, highest oxygen delivery flow rate (if receiving noninvasive oxygen), highest fraction of inspired oxygen (% FiO₂) (if on positive pressure ventilation), highest positive end-expiratory pressure (if on positive pressure ventilation), and lowest partial pressure of oxygen (PaO₂):fraction of inspired air (FiO₂) ratio if arterial blood gas is obtained and the patient is on positive pressure ventilation.

8.13 Echocardiogram

An echocardiogram (ECHO) is not necessary unless otherwise indicated. An up-trending troponin-I with hemodynamic compromise or other concerning cardiovascular symptoms/signs should prompt consideration of obtaining an ECHO.

9 STATISTICS

9.1 Analysis Populations

All computations will be performed using SAS[®] Version 9.4 or higher.

The following analysis populations will be defined for this study:

- Intent-to-Treat (ITT) Population: All patients who are randomized;
- Safety Population: All randomized patients who receive at least 1 dose of study drug; and
- Per Protocol (PP) Population: All patients in the ITT Population who finish the study as designed and without major protocol deviations.

Efficacy and safety data will be summarized by treatment arm. Data from all enrolled cohorts will be pooled together for analysis and sequentially analyzed in subgroups.

The ITT Population will be used to examine efficacy for both the primary and secondary endpoints, the Safety Population will be used to assess safety endpoints, and the PP Population will be used as a secondary population for the analysis of the primary efficacy endpoint. A list of patients with major protocol deviations leading to exclusion from the PP Population will be finalized prior to unblinding the randomized treatment assignments. All timepoints for analysis purposes will be collected from the day of randomization.

9.2 Statistical Methods

9.2.1 Analysis of Efficacy

9.2.1.1 Primary efficacy endpoint

The time to achieve a ≥ 2 -point increase in the NIAID 8-point ordinal scale from baseline by Day 29 will be analyzed using the Cochran-Mantel-Haenszel (CMH) test adjusting for the baseline NIAID 8-point ordinal scale. The NIAID 8-point ordinal scale will be assessed daily while the patient is hospitalized. If the patient remains hospitalized, the scale will also be assessed on Days 15 and 29. Any patient in the ITT Population with a missing primary endpoint result will be considered as a non-responder. The point estimates of the time to achieve a ≥ 2 -point increase will be presented by treatment arm together with their 95% confidence intervals. The CMH odds ratio, associated 95% confidence interval, and p-value will also be presented.

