DOSAGE FORMS AND ROUTE OF ADMINISTRATION:

EFFICACY ENDPOINTS:

Primary Efficacy Endpoint

The primary efficacy endpoint is the time to achieve a ≥ 2 -point increase in the National Institute of Allergy and Infectious Diseases (NIAID) 8-point ordinal scale from baseline by Day 29.

The NIAID 8-point ordinal scale includes the following grades:

1. Death;
2. Hospitalized, on invasive mechanical ventilation or extracorporeal membrane oxygenation;

3. Hospitalized, on non-invasive ventilation or high-flow oxygen devices;
4. Hospitalized, requiring supplemental oxygen;
5. Hospitalized, not requiring supplementation oxygen – requiring ongoing medical care (COVID-19 related or otherwise);
6. Hospitalized, not requiring supplemental oxygen – no longer requires ongoing medical care;
7. Not hospitalized, limitation on activities and/or requiring home oxygen; and
8. Not hospitalized, no limitations on activities.

Secondary Efficacy Endpoints

The secondary efficacy endpoints, listed in hierarchical order, include the following:

- Time to achieve a ≥ 2 -point decrease in the NIAID 8-point ordinal scale;
- Length of hospital stay from first dosing (Day 1) and percentage of patients who have recovered and been discharged from the hospital by Days 15 and 29;
- Mortality rate by Days 15 and 29;
- Proportion of patients with a ≥ 2 -point increase in the NIAID 8-point ordinal scale from baseline to Days 15 and 29;
- Alive and respiratory failure free days by Days 15 and 29;
- Percentage of patients progressed to severe/critical disease by Day 15; and
- Occurrence of any new infections during the study by Day 29.

SAFETY ENDPOINTS:

The safety endpoints include the following:

- All cause treatment-emergent adverse events (TEAEs) and serious adverse events (SAEs);
- Change from screening (baseline) in clinical symptoms and abnormal vital signs, abnormal laboratory tests (e.g., complete blood count, serum chemistry, routine urinalysis, and coagulation function), and 12-lead electrocardiograms (ECGs); and
- Relationship of any observed adverse events (AEs) with F-652 treatment based on the Investigator's judgement.

STATISTICAL ANALYSES:

All computations will be performed using SAS® Version 9.4 or higher.

The following analysis populations will be defined for this study:

- Intent-to-Treat (ITT) Population: All patients who are randomized;
- Safety Population: All randomized patients who receive at least 1 dose of study drug; and

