- Per Protocol (PP) Population: All patients in the ITT Population who finish the study as designed and without major protocol deviations.

Efficacy and safety data will be summarized by treatment arm. Data from all enrolled cohorts will be pooled together for analysis and sequentially analyzed by subgroups.

The ITT Population will be used to examine efficacy for both the primary and secondary endpoints, the Safety Population will be used to assess the safety endpoints, and the PP Population will be used as a secondary population for the analysis of the primary efficacy endpoint.

Efficacy Analyses

Primary efficacy endpoint

The time to achieve a ≥ 2 -point increase in the NIAID 8-point ordinal scale from baseline by Day 29 will be analyzed using the Cochran-Mantel-Haenszel (CMH) test adjusting for the baseline NIAID 8-point ordinal scale. The NIAID 8-point ordinal scale will be assessed daily while the patient is hospitalized. If the patient remains hospitalized, the scale will also be assessed on Days 15 and 29. Any patient in the ITT Population with a missing primary endpoint result will be considered as a non-responder. The point estimates of the time to achieve a ≥ 2 -point increase will be presented by treatment arm together with their 95% confidence intervals. The CMH odds ratio, associated 95% confidence interval, and p-value will also be presented.

Secondary efficacy endpoints

The time to achieve a ≥ 2 -point decrease in the NIAID 8-point ordinal scale, proportion of patients with a ≥ 2 -point increase in the NIAID 8-point ordinal scale from baseline to Days 15 and 29, mortality rate by Days 15 and 29, percentage of patients who have recovered and been discharged from the hospital by Days 15 and 29, and percentage of patients progressed to severe/critical disease by Day 15 will be analyzed using the same method as described for the primary efficacy endpoint.

The number of alive and respiratory failure free days by Days 15 and 29, the length of hospital stay from first dosing (Day 1) to discharge by Days 15 and 29, and occurrence of any new infections during the study by Day 29 will be summarized using descriptive statistics.

Exploratory Endpoints

The exploratory endpoints will be summarized using descriptive statistics.

Safety Analyses

All safety analyses will be performed on the Safety Population.

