9.2.1.2 Secondary efficacy endpoints

The time to achieve a ≥ 2 -point decrease in the NIAID 8-point ordinal scale, proportion of patients with a ≥ 2 -point increase in the NIAID 8-point ordinal scale from baseline to Days 15 and 29, mortality rate by Days 15 and 29, percentage of patients who have recovered and been discharged from the hospital by Days 15 and 29, and percentage of patients progressed to severe/critical disease by Day 15 will be analyzed using the same method as described for the primary efficacy endpoint in Section 9.2.1.1.

The number of alive and respiratory failure free days by Days 15 and 29, the length of hospital stay from first dosing (Day 1) to discharge by Days 15 and 29, and occurrence of any new infections during the study by Day 29 will be summarized using descriptive statistics.

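### The primary endpoint is a time to improvement, but its CMH test and odds ratio read most naturally as a yes/no comparison at Day 29

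*Combined protocol and SAP*

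**What the plan says.** The synopsis and section 7.1.1 use the same definition: "The primary efficacy endpoint is the time to achieve a" gain of 2 or more points on the NIAID scale from baseline, by Day 29. Grade 1 is death and grade 8 is full activity at home, so an increase is an improvement.

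For the analysis, section 9.2.1.1 and the synopsis say that this time "will be analyzed using the Cochran-Mantel-Haenszel (CMH) test adjusting for the baseline NIAID 8-point ordinal scale". They add that "The CMH odds ratio, associated 95% confidence interval, and p-value will also be presented" and that "Any patient in the ITT Population with a missing primary endpoint result will be considered as a non-responder". Point estimates of the time "will be presented by treatment arm together with their 95% confidence intervals", but no estimator is named and no between-arm comparison of times is attached to them.

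Section 9.2.1.2 lists several secondary endpoints that "will be analyzed using the same method as described for the primary efficacy endpoint in Section 9.2.1.1". They include plain proportions, among them the proportion with the same 2-point gain to Days 15 and 29. They also include a second time endpoint, the time to a drop of 2 or more points.

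**The concern.** An odds ratio and a non-responder rule describe an outcome that either happened or did not. A time endpoint needs a time or rank for patients who never improve, or a set of patients at risk on each day, and a measure of effect on time. The protocol gives none of these, although the scale is scored daily in hospital.

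If the test is the yes/no CMH, the primary p-value does not address the endpoint it is named for. It also largely repeats the secondary Day-29 proportion, differing mainly for patients who improve and then relapse. Speed of recovery would then appear only in the Day-15 proportions and in descriptive summaries, such as the by-arm times and "the length of hospital stay from first dosing (Day 1) to discharge by Days 15 and 29". If another CMH layout is meant, the protocol does not say which, so the primary p-value is not uniquely pre-specified.

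**Working it through.** The plan has no power figure to reproduce, because section 9.2.5 says the sample size was not based on power. The cohorts add up: 4 + 14 + 4 + 16 = 38, and 2 + 7 + 2 + 8 = 19 per arm.

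**1. What each CMH layout would compare**

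| Layout | Compares times? | Gives an odds ratio? | Would also need |
|---|---|---|---|
| One 2×2 table (improved by Day 29, yes/no) per baseline grade | No | Yes | Nothing further |
| Mean-score test on ranked times | Yes | No | A rank for non-responders |
| One 2×2 table per event day within grade (equal to the log-rank) | Yes | Yes, pooled | Day strata and risk sets |

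Only the first needs nothing that the protocol leaves out. It is also the layout that suits the proportions in section 9.2.1.2.

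**2. A constructed example** (one baseline stratum, 19 per arm, 16 improvers in each arm; drug patients improve on Days 3 to 18, placebo patients on Days 11 to 26)

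- Median time is the 10th of 19 ordered times: Day 12 against Day 20.
- Yes/no CMH: observed minus expected = 16 − 19 × 32/38 = 0, so chi-square = 0 and p = 1.00. Odds ratio = (16 × 3)/(3 × 16) = 1.00.
- Day-by-day CMH (log-rank): observed 16, expected 11.08, variance 6.90. Chi-square = (16 − 11.08)²/6.90 = 3.51, p = 0.061. Pooled Mantel-Haenszel odds ratio = 9.51/4.59 = 2.07.

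The same data give p = 1.00 or p = 0.061, depending on a layout that the protocol does not state.

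**3. The odds ratio does not track an effect on time.** With a proportional rate ratio of 2, the response on drug is p1 = 1 − (1 − p0)², and the odds ratio is [p1/(1 − p1)]/[p0/(1 − p0)]. At p0 = 50%, p1 = 75% and the odds ratio is 3.0. At 70%, 80% and 90% it is 4.3, 6.0 and 11.0. One effect on time thus gives very different odds ratios.

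**4. Power, by simulation.** Everything here except the 19 per arm is an assumption: two-sided 5%; three equally likely baseline grades with 1.5-fold steps in rate; exponential times in whole days cut at 28 days; 4,000 trials per setting.

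| Placebo response by Day 29 | Yes/no CMH, rate ratio 2 | Stratified log-rank, rate ratio 2 | Yes/no CMH, late effect | Stratified log-rank, late effect |
|---|---|---|---|---|
| 30% | 24% | 25% | 25% | 21% |
| 50% | 31% | 35% | 32% | 23% |
| 70% | 30% | 42% | 33% | 19% |
| 80% | 26% | 46% | 26% | 13% |
| 90% | 9% | 46% | 9% | 8% |

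The late effect is a rate ratio of 3 after Day 14 only. Simulation error is about 0.8 points at 40–50% power. A separate run at rate ratio 2 with two equal baseline strata gave somewhat higher levels for most entries and the same pattern: CMH against log-rank 37 against 39% at 50% response, and 10 against 49% at 90%.

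**The case against.** The strongest reply is that a CMH test can compare times. This is correct: taken over event days it is the log-rank test, it can hold non-responders at risk to Day 29, and it yields a pooled odds ratio. A reader might infer from the odds ratio that no reading of the text can be made coherent. The day-by-day layout shows that this goes too far. It is still not the natural reading, because the protocol mentions no day strata, ranks or risk sets.

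Second, section 9.2.3 leaves full technical details to a formal SAP due before database lock. That SAP could name the layout and the time estimator, but the supplied text does not contain it, and the protocol already fixes the test and the effect measure.

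Third, the by-arm times with confidence intervals would show a difference in timing. They would, but only descriptively.

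Fourth, the log-rank test is not better in every case. It has less power for a late-only effect. For a pure speed effect with equal Day-29 proportions the CMH stays at 4–5%, and the log-rank reaches only 6–8% at 50% response, 8–16% at 70% and 16–50% at 90%, depending on the assumed time distribution. This stands, and it is why both remedies are offered on equal terms.

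**Conclusion.** The mismatch is real and can be seen from the text alone. The endpoint is a time; the test and effect measure read most naturally as yes/no; and the alternatives that would compare times are not specified. The same applies to the time to a 2-point drop.

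The cost in power depends on assumed rates. At a rate ratio of 2 it is small at 30–50% placebo response, about 10–12 points at 70%, about 20 at 80% and 35 or more at 90%. It reverses if the effect comes only late. The documents give no response rate, so the trial cannot be placed within this range.

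Two stronger conclusions are not supported. One is that the sample size or power is wrong: section 1.5 calls the study exploratory and section 9.2.5 claims no power. The other is that Day-29 grades will be missing after discharge. A reader might infer it from "If the patient remains hospitalized, the scale will also be assessed on Days 15 and 29", but the synopsis and section 3.1 place efficacy assessments on Days 15 and 29 without that condition, grades 7 and 8 describe patients at home, and the Schedule of Procedures is not shown in the text supplied.

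**What to change.** Before unblinding, choose one option and carry it through section 9.2.1.1, section 9.2.1.2 and the synopsis.

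- **(a) Keep the time endpoint.** Make the primary test a log-rank test stratified by baseline NIAID grade (equivalently, a CMH test over event days). Report Kaplan-Meier or cumulative-incidence times with 95% confidence intervals and a stratified rate ratio. Keep the spirit of the non-responder rule by holding patients who die or withdraw without improving as not improved to Day 29, and censor withdrawals in a sensitivity analysis. With 10% random withdrawal, holding instead of censoring costs at most about 2 points of power (39.3 against 41.1% at 70% response). Informative withdrawal was not simulated.
- **(b) Keep the yes/no CMH and odds ratio.** Rename the primary endpoint as the proportion improved by Day 29, and state how it differs from the secondary Day-29 proportion.

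Treat the time to a 2-point drop consistently with the choice, and keep the CMH for the proportion endpoints under either option.

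The cost is wording plus some programming before database lock, with no extra patients. Option (a) has less power if the effect appears only late; option (b) gives up a test of speed.

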9.2.1.2 Secondary efficacy endpoints

The time to achieve a ≥ 2 -point decrease in the NIAID 8-point ordinal scale, proportion of patients with a ≥ 2 -point increase in the NIAID 8-point ordinal scale from baseline to Days 15 and 29, mortality rate by Days 15 and 29, percentage of patients who have recovered and been discharged from the hospital by Days 15 and 29, and percentage of patients progressed to severe/critical disease by Day 15 will be analyzed using the same method as described for the primary efficacy endpoint in Section 9.2.1.1.

The number of alive and respiratory failure free days by Days 15 and 29, the length of hospital stay from first dosing (Day 1) to discharge by Days 15 and 29, and occurrence of any new infections during the study by Day 29 will be summarized using descriptive statistics.

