Treatment will begin on Day 1 following randomization. Patients assigned to active drug will receive a total of 2 doses of F-652 (1 IV infusion on Day 1 and 1 IV infusion on Day 8). Patients assigned to placebo will receive identical IV infusions of placebo vehicle on Days 1 and 8. If the patient is discharged from the site prior to Day 8, they will return for an outpatient visit to receive the second IV infusion and remain at the site for an approximate 2-hour observation period. All patients will receive available supportive and antiviral therapies as standard of care. Efficacy will be assessed on Days 15 and 29. Patients will be followed for safety until Day 60.

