4.3.1 Criteria for Discontinuation of Dosing in Individual Patients

Patients will be discontinued from dosing but will continue to be followed in the study if they experience any of the following:

- \geq Grade 3 (CTCAE v5.0) AE or clinically significant laboratory abnormality considered related to study drug;
- \geq Grade 3 (CTCAE v5.0) infusion reaction in the first 24 hours post-infusion;
- \geq Grade 2 (CTCAE v5.0) cytokine release syndrome;
- \geq Grade 2 skin-related AEs;
- Severe anaphylactic reaction, including bronchospasm; and/or
- Progression to acute respiratory distress syndrome.

For any patient who prematurely discontinues from study treatment, the reason and date of discontinuation will be documented in the electronic case report form (eCRF) and the patient should continue study visits and procedures as outlined in the Schedules of Procedures ([Appendix A](#)).

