7.1.2 Secondary Efficacy Endpoints

The secondary efficacy endpoints, listed in hierarchical order, include the following:

- Time to achieve a ≥ 2 -point decrease in the NIAID 8-point ordinal scale;
- Length of hospital stay from first dosing (Day 1) and percentage of patients who have recovered and been discharged from the hospital by Days 15 and 29;
- Mortality rate by Days 15 and 29;
- Proportion of patients with a ≥ 2 -point increase in the NIAID 8-point ordinal scale from baseline to Days 15 and 29;
- Alive and respiratory failure free days by Days 15 and 29;
- Percentage of patients progressed to severe/critical disease by Day 15; and
- Occurrence of any new infections during the study by Day 29.

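### Length of stay has no defined value for in-hospital deaths, and the Per Protocol completion condition can drop patients because of their outcome (minor)

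*Combined protocol and SAP*

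**What the plan says.** **Length of stay.** Section 7.1.2 lists it inside the second of the ranked secondary endpoints: "Length of hospital stay from first dosing (Day 1) and percentage of patients who have recovered and been discharged from the hospital". That listing names the start of the stay but not its end. Section 9.2.1.2 supplies the end, "the length of hospital stay from first dosing (Day 1) to discharge by Days 15 and 29", and assigns descriptive statistics only; the synopsis has the same text. Neither gives a value to a patient who dies in hospital or is still there at the cut-off. The non-responder rule in Section 9.2.1.1 is worded for the primary endpoint and yields no number of days. Section 9.2.1.2 extends the primary method to other secondary endpoints but not to this one.

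**Per Protocol.** Section 9.1 and the synopsis define it as "All patients in the ITT Population who finish the study as designed and without major protocol deviations", and "the PP Population will be used as a secondary population for the analysis of the primary efficacy endpoint". Section 3.1 adds: "Patients will be followed for safety until Day 60". Section 4.4 allows withdrawal from the study for a serious or clinically significant adverse event and says that safety withdrawals are not replaced. Section 4.3.1 treats stopping of dosing separately: "Patients will be discontinued from dosing but will continue to be followed in the study if they experience any of the following". One listed reason is "Progression to acute respiratory distress syndrome". Section 9.1 has the list of exclusions for major deviations finalised before unblinding. Section 10.3 defines completion for the trial as a whole, not for a patient.

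**The concern.** Both rules make inclusion depend on something that happens after randomisation and is tied to outcome.

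For length of stay, whoever programs the table must choose what to do with deaths. Leaving them out restricts the summary to survivors. Ending the stay at death makes an early death look like a short stay. Either way, an arm with more deaths can look equal or better on this measure.

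For Per Protocol, a patient who dies or is withdrawn before Day 60 has not completed the study in the ordinary sense. Such a patient leaves the analysis even if the Day 29 endpoint was fully observed. Whether a patient whose dosing was stopped under Section 4.3.1 still counts as following the design is not stated, and one reason for stopping is itself clinical worsening. The secondary analysis of the primary endpoint may then differ from ITT because of who was removed, not because of adherence. The blinded list keeps exclusions for deviations from being chosen by arm, but it does not remove a condition on completing follow-up.

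**Working it through.** **Sample size.** Section 9.2.5: 4 + 14 + 4 + 16 = 38. The synopsis gives 2 + 7 + 2 + 8 = 19 per arm. Both agree with the plan, which states no power calculation. Every death count, stay, loss rate and response rate below is an assumption; the documents give none.

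**Step 1: Day 29 mean stay with deaths.** Assume survivors are discharged after 12 days and deaths occur after 6. The full window is 29 − 1 = 28 days. With d deaths among 19:
- deaths left out: mean = 12, whatever d is
- stay ended at death: mean = (12(19 − d) + 6d)/19
- deaths given the full window: mean = (12(19 − d) + 28d)/19

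For 3 deaths against 1:
- ended at death: 210/19 − 222/19 = 11.05 − 11.68 = −0.63
- full window: 276/19 − 244/19 = 14.53 − 12.84 = +1.68

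Difference in mean days, arm with more deaths minus the other:

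| Deaths | Left out | Ended at death | Full window |
|---|---|---|---|
| 2 vs 1 | 0 | −0.3 | +0.8 |
| 3 vs 1 | 0 | −0.6 | +1.7 |
| 5 vs 1 | 0 | −1.3 | +3.4 |
| 3 vs 3 | 0 | 0 | 0 |

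The sign depends on a rule that the plan does not state. With equal deaths and the same timing there is no difference.

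**Step 2: the median.** In Step 1 the median is 12 throughout, but only because all survivors were given the same stay. Take instead 19 assumed stays: 4, 5, 5, 6, 6, 7, 7, 8, 8, 9, 10, 11, 12, 14, 16, 18, 21, 24, 27. The mean is 218/19 = 11.5 and the median 9. Let the three longest be deaths:
- left out: mean 146/16 = 9.1, median 8
- ended after 6 days: mean (146 + 18)/19 = 8.6, median 7
- time to live discharge, deaths held as not discharged: 16/19 = 84.2% discharged. The tenth of 19 patients leaves after 9 days, so the median is 9.

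The first two rules make this arm look faster after three deaths. The third does not.

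**Step 3: Day 15, no deaths.** This applies only if the text is not read as truncation. Assume discharged patients stay 9 days, with 10 against 15 discharged by Day 15. Discharged only: 9.0 vs 9.0. Giving the rest 15 − 1 = 14 days: (10×9 + 9×14)/19 = 11.4 vs (15×9 + 4×14)/19 = 10.1, a difference of 25/19 = 1.3 days. With 12 against 14 discharged it is 10/19 = 0.5; with 12 against 12 it is 0.

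**Step 4: Per Protocol.** Take response as a simple proportion by Day 29, unstratified. Assume ITT response of 12/19 = 63.2% in both arms. The difference is 0, with 95% half-width 1.96 × √(2 × 0.632 × 0.368/19) = 30.7 points. If all dropped patients are non-responders:
- 1 vs 1 dropped: 12/18 − 12/18 = 0
- 2 vs 1: 12/17 − 12/18 = +3.9 points
- 3 vs 1: 12/16 − 12/18 = +8.3 points
- 4 vs 1: 12/15 − 12/18 = +13.3 points

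The arm that loses more patients looks better. If the dropped patients had already responded (late death or withdrawal), the shift reverses: 3 vs 1 gives 9/16 − 11/18 = −4.9 points.

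**Step 5: how likely a loss is.** If a patient dies or is withdrawn for safety with probability 5%, 10% or 20%, the expected losses are 38 × p = 1.9, 3.8 or 7.6. The chance of at least one loss in an arm is 1 − (1 − p)^19 = 62.3%, 86.5% or 98.6%.

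**The case against.** The strongest reply is that little depends on either measure. Length of stay is descriptive and untested. It shares its bullet with the percentage discharged, and mortality is the next bullet. Both are analysed in ITT, where an in-hospital death cannot count as a discharge. A reader might infer that deaths are concealed; the documents do not support that, since only the length-of-stay figure itself can mislead.

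A reader might also infer that patients still in hospital necessarily have no value. That goes too far: the reference to Days 15 and 29 can be read as truncation, which would give them one. The text does not say so, and truncation alone would not settle how deaths count.

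On Per Protocol, excluding non-completers is common and the population is expressly secondary. Stopping dosing with continued follow-up is part of the design, so it would be wrong to say that every patient stopped under Section 4.3.1 is excluded; their status is unclear. The illustrated shifts need unequal losses and lie inside an interval of about ±31 points.

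Finally, Section 9.2.3 defers technical detail to a formal statistical analysis plan before database lock. Its text is not in the document, so it may settle both points.

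These replies limit the importance. They do not supply a value for an in-hospital death, or a reason to tie a Day 29 analysis to completion of Day 60 follow-up.

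**Conclusion.** The point holds, and it is minor. Length of stay gives in-hospital deaths no valid value, and the Per Protocol completion condition, read literally, drops deaths and safety withdrawals. Both can partly select on outcome.

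On assumed counts, the difference in mean stay moves by up to a few days and changes sign with the unstated rule. Per Protocol response moves by roughly 4 to 13 points when non-responders are lost unequally, and can move the other way when responders are lost. These figures show direction and order of size, not expected results. A difference between arms needs unequal deaths, discharges or losses, or unequal timing of them.

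A reader might infer that the trial's main efficacy result is biased. The documents do not support that: efficacy is analysed in ITT, and neither rule touches the ITT primary analysis.

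**What to change.** **Section 9.2.1.2 and synopsis.** Replace length of stay with time from first dosing to live discharge. Hold deaths as not discharged through the cut-off (Day 15 or Day 29), and censor patients still in hospital at that cut-off. Report the number of deaths and continued stays per arm beside it. Cost: the median may not be reached in an arm, and the stay will look longer.

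**Section 9.1 and synopsis.** Remove the completion condition. Define Per Protocol by eligibility, study drug received while dosing was permitted, and no major deviation affecting the primary endpoint through Day 29. State that death, safety withdrawal, or stopping dosing under a protocol rule does not by itself exclude a patient, and that death without prior improvement counts as non-response. Cost: Per Protocol will differ less from ITT.

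Both are wording changes, to be carried into the statistical analysis plan before unblinding. They need no extra patients or visits.
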